11.6.1.2.4 PROGRESSION FREE SURVIVAL

The median PFS and the probability of subjects alive and progression-free during the first 6, 12, 18, and 24 cycles will be estimated using the Kaplan-Meier method. PFS is defined as the interval between enrollment and the earlier of date of progression or death due to any cause. For each estimate, a 95% confidence interval will be reported. For subjects who are alive without definitive disease progression, it will be censored at the last assessment.

11.6.1.2.5 TIME TO SECOND OBJECTIVE DISEASE PROGRESSION (PFS2)

PFS2 is defined as the interval from enrollment to the earlier of the first documentation of definitive disease progression on next-line treatment or death from any cause. The median duration of PFS2 and the probability of subjects who are alive and do not have progression on next-line treatment during the first 6, 12, 18 and 24 cycles will be estimated using the Kaplan-Meier method. For subjects alive without definitive disease progression on next-line treatment (including subjects who are alive and do not have next-line treatment), it will be censored at the last assessment.

Definitive disease progression based on standard criteria (Hallek, et al., 2018) and occurring for any reason (i.e., increasing lymphadenopathy, organomegaly or bone marrow involvement; decreasing platelet count, hemoglobin, or neutrophil count; or worsening of disease-related symptoms). Note that lymphocytosis in the absence of other evidence of disease progression does not constitute disease progression.

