Dosing Regimen & Treatment Study Visits	
progression, unacceptable toxicity, or withdrawal from the study due to investigator decision or other reasons. Subjects who complete 24 cycles of treatment and remain D-MRD (MRD positive), or those who discontinue study treatment and have not progressed will enter a period of treatment-free observation. Subjects entering treatment-free observation with D-MRD, no PB MRD assessment is required during TFO.
 
All subjects (whether U-MRD or D-MRD following treatment) who subsequently develop clinical progression requiring treatment per iwCLL criteria (Hallek, et al., 2018) will be retreated with the same triple combination regimen previously received, provided that clinical progression occurs after 6 months of treatment-free observation. Retreatment will not be initiated upon achieving MRD positivity, but only upon clinical progression requiring treatment per iwCLL criteria. Subjects who progress within 6 months of treatment-free observation will be considered refractory and discontinue from the study.
																		
	Cohort A: Ublituximab and Umbralisib with Ibrutinib																		
	Cycle 1:																		
	
  
 Ublituximab	Umbralisib	Ibrutinib			
   
 Day 1	Day 2	Day 8 & 15	Daily	Daily	
 
 150 mg	750 mg	900 mg	800 mg	previously tolerated dose	
  
					Ublituximab	Umbralisib	Ibrutinib			Day 1	Day 2	Day 8 & 15	Daily	Daily	150 mg	750 mg	900 mg	800 mg
Ublituximab	Umbralisib	Ibrutinib																	
Day 1	Day 2	Day 8 & 15	Daily	Daily															
150 mg	750 mg	900 mg	800 mg	previously tolerated dose															
Cycles 2 through 6:																			

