3.2 EFFICACY ENDPOINTS

Undetectable Minimal Residual Disease (U-MRD) Rate

U-MRD rate is defined as the proportion of subjects who have undetectable MRD in the peripheral blood as confirmed by central lab.

Time to U-MRD

Time to undetectable minimal residual disease is defined as the interval from enrollment to the first assessment of U-MRD.

Overall response rate (ORR)

ORR is defined as sum of CR and PR rates.

Complete Response (CR) Rate

CR rate is defined as the proportion of subjects who achieve a CR.

Progression-free survival (PFS)

[figure not shown]
PFS is defined as the interval from enrollment to the earlier of the first documentation of definitive disease progression or death from any cause.

Definitive disease progression based on standard criteria (Hallek, et al., 2018) and occurring for any reason (i.e., increasing lymphadenopathy, organomegaly or bone marrow involvement; decreasing platelet count, hemoglobin, or neutrophil count; or worsening of disease-related symptoms). Note that lymphocytosis in the absence of other evidence of disease progression does not constitute disease progression.

Time to second objective disease progression (PFS2)

PFS2 is defined as the interval from enrollment to the earlier of the first documentation of definitive disease progression on next-line treatment or death from any cause.

Definitive disease progression based on standard criteria (Hallek, et al., 2018) and occurring for any reason (i.e., increasing lymphadenopathy, organomegaly or bone marrow involvement; decreasing platelet count, hemoglobin, or neutrophil count; or worsening of disease-related symptoms). Note that lymphocytosis in the absence of other evidence of disease progression does not constitute disease progression.

Duration of U-MRD response

Duration of U-MRD response is defined as the interval from the first documentation of undetectable MRD to the earlier of the first documentation of presence of MRD or death from any cause.

Treatment-free survival (TFS)

TFS is defined as the interval from drug discontinuation to the earlier of initiation of retreatment for disease progression requiring treatment or death from any cause.

Disease progression requiring treatment is based on standard criteria (Hallek, et al., 2018)

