5.6 DISCONTINUATION FROM STUDY

Subjects will be discontinued from the study for any of the following reasons:

- Disease progression while on study treatment
- Disease progression within 6 months during treatment-free observation
- Subject requests to withdraw consent or discontinue treatment
- Pregnancy
- Inability of the subject to comply with study requirements
- Conditions requiring therapeutic intervention not permitted by the protocol
- Non-compliance/lost to follow-up
- Investigator discretion
- Discontinuation of the study by the Sponsor

Subjects who discontinue from study treatment (for reasons other than progressive disease) will continue to be followed for progression and survival for 24 months.

After withdrawal from study, subjects should be followed for AEs for 30 calendar days after their last dose of either study drug. All new AEs occurring during this period must be reported and followed until resolution, unless, in the opinion of the investigator, these values are not likely to improve because of the underlying disease. In this case the investigators must record his or her reasoning for this decision in the subject's medical records and as a comment on the electronic Case Report Form (eCRF).

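### PFS2 needs data from after first progression, but early progressors leave the study without next-line or survival follow-up, so their censoring is informative and PFS2 is biased upward

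*Combined protocol and SAP*

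**What the plan says.** Sections 3.2 and 11.6.1.2.5 measure PFS2 from enrollment to "the earlier of the first documentation of definitive disease progression on next-line treatment or death from any cause". The curve is Kaplan-Meier, with a median and probabilities "during the first 6, 12, 18 and 24 cycles will be estimated using the Kaplan-Meier method". The censoring rule is "For subjects alive without definitive disease progression on next-line treatment (including subjects who are alive and do not have next-line treatment), it will be censored"; the date used is that of the last assessment. Neither section defines next-line treatment.

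Section 5.6 lists the reasons for leaving the study. One is progression while on study treatment. Another is "Disease progression within 6 months during treatment-free observation". The synopsis repeats the second: "Subjects who progress within 6 months of treatment-free observation will be considered refractory and discontinue from the study". Section 5.6 then says who is followed afterwards: "Subjects who discontinue from study treatment (for reasons other than progressive disease) will continue to be followed for progression and survival for 24 months".

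Once a subject has withdrawn, Section 5.6 asks for adverse events to 30 days after the last dose. Section 12.5.3 adds that only treatment-related AEs, SAEs or deaths are reported beyond that. On-study re-treatment (synopsis, Sections 5.2 and 5.4) is open only to subjects whose progression comes after 6 months of observation.

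**The concern.** An endpoint about second progression needs data from after the first. The subjects removed under Section 5.6 have just failed on treatment or soon after stopping it, and the protocol itself calls the latter group refractory. Kaplan-Meier treats a censored subject as having the same later risk as those still under observation. Here the trigger for censoring is the failure itself.

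Subjects still at risk without a first progression can have a PFS2 event only by dying, until they too progress and are treated again. The removed subjects have already used up the first step, so their later hazard is very likely higher and the bias runs upward. At stake is a stated secondary objective: the reported curve would mainly describe subjects who did well enough to stay on study. Data that were never collected cannot be recovered at analysis.

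**Working it through.** **What is collected on an early progressor**

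| Needed for PFS2 | Where it might be collected | Result |
|---|---|---|
| Start and name of next-line therapy | Schedules 7.1 and 7.2 | No post-progression visit or item |
| Progression on next-line therapy | Section 5.6, 24-month follow-up | Excludes those stopped for progression |
| Same | Section 8.4, follow-up after drug discontinuation | Covers follow-up to progression, not after it |
| Same | Section 7.3, long-term follow-up column | Re-treatment schedule only |
| Death | Sections 12.5.3, 12.6.2, 12.9.3 | Safety reporting to 30 days, then treatment-related only |

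So the last assessment used for censoring falls at about the first progression.

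**Size, by illustration.** The plan gives no PFS2 estimate or progression rate, so there is no figure to reproduce. Only the landmarks come from the documents: 6, 12, 18 and 24 cycles of 28 days are days 168, 336, 504 and 672. Dividing by 30.4375 gives t = 5.52, 11.04, 16.56 and 22.08 months.

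Assumptions:
- A proportion p progress early, with first progression uniform over months 3 to 24.
- Time from then to second progression or death is exponential with median m months.
- Everyone else has no PFS2 event before month 30.

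Under these assumptions the as-written curve stays at 100% at all four landmarks. For t up to 24 months the events missed are

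overstatement(t) = (p / 21) × { (t − 3) − (m / ln 2) × [1 − 2^(−(t − 3)/m)] }.

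With p = 0.20 and m = 12, m / ln 2 = 17.31. At 24 cycles t − 3 = 19.08 and 2^(−19.08/12) = 0.332. The bracket is 19.08 − 17.31 × 0.668 = 7.52, and 0.20 × 7.52 / 21 = 0.072.

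| Landmark | t − 3 (months) | Bracket | Overstatement | True PFS2 |
|---|---|---|---|---|
| 6 cycles | 2.52 | 0.175 | 0.2 points | 0.998 |
| 12 cycles | 8.04 | 1.608 | 1.5 points | 0.985 |
| 18 cycles | 13.56 | 4.157 | 4.0 points | 0.960 |
| 24 cycles | 19.08 | 7.517 | 7.2 points | 0.928 |

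Overstatement at 24 cycles, in percentage points:

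| Early progressors | m = 6 | m = 12 | m = 24 |
|---|---|---|---|
| 5% | 2.7 | 1.8 | 1.1 |
| 10% | 5.4 | 3.6 | 2.1 |
| 20% | 10.8 | 7.2 | 4.2 |
| 30% | 16.3 | 10.7 | 6.3 |

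In a cohort of 28, 20% is 5.6 subjects, so about 6 would be lost this way.

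**Cross-check with a different model.** A simulation used exponential first progression (10, 20 or 40% by 24 cycles), 5% deaths by 24 cycles, and 30% or 60% stopping early for U-MRD. All of these rates are assumed. The as-written estimate exceeded the true one in every scenario, by 2.4 to 24.7 points at 24 cycles and about 6 to 35 points at 48 months. With 40% progressing and a next-line median of 6 or 12 months, the true median PFS2 was 42 to 52 months, while the as-written median was not reached.

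**Lower bound.** Counting each early progressor as an event at first progression gives, at 24 cycles in the base case, 1 − 0.20 × 19.08 / 21 = 0.818. The true 0.928 lies between this and the as-written 1.000.

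**The case against.** The case for leaving it alone is reasonable on weight. PFS2 is one of several secondary measures in an open-label trial whose cohorts, of up to about 28, are evaluated separately, with no PFS2 test, power statement or decision rule. Early failure is not hidden, because each early progressor is an event in PFS. Every rate above is assumed. Inclusion requires at least stable disease on the current agent, so early progression may be uncommon. All of this stands, and it lowers the severity. It does not remove the gap between Sections 5.6 and 11.6.1.2.5.

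Some stronger readings are tempting but not supported.

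- A reader might infer that the early landmarks prove bias. Confirmed U-MRD at Cycle 4 means stopping at day 112, with re-treatment no sooner than day 112 + 183 = 295. A 24-cycle completer cannot start before 672 + 183 = 855. So on-study re-treatment cannot produce a second progression by day 168. But true PFS2 at 6 cycles is also close to 100% (0.998 in the base case), and a completer without progression really has had no second progression by day 672.
- A reader might infer that PFS2 will look best where early failures are most frequent. In the illustration the as-written value does not move with the early-failure rate; only the overstatement grows.
- A reader might infer that nothing at all is collected. Safety reporting runs to 30 days and treatment-related deaths are reportable later. Section 12.6.2 also sends unrelated CLL progression to an eCRF. What is missing is next-line therapy, progression on it, and general survival.
- A reader might take re-treated subjects as certain to supply second progressions. That holds only if protocol re-treatment counts as next-line treatment, which is not stated.

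**Conclusion.** The plan as written gives an informatively censored PFS2. The upward direction rests on one assumption: that subjects removed for early progression have a higher later event rate than those still at risk.

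The size cannot be derived from the documents. In the base-case illustration it is negligible at 6 cycles and about 7 points at 24 cycles, with a 24-cycle range of about 1 to 16 points over the grid shown. It grows later and can affect the median. The primary U-MRD rate and PFS do not depend on post-progression data and are unaffected. This is a should-fix, not a must-fix.

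**What to change.** **Data collection.** In Section 5.6, and in the matching text of the synopsis, Section 5.4 and the Section 7 schedules, separate stopping protocol treatment from leaving the study. Keep early progressors in remote follow-up, by record review or telephone, for: start date and name of next-line therapy, date of progression on it, and date of death.

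**Analysis.** In Section 11.6.1.2.5, define next-line treatment, including whether protocol re-treatment counts, and use the new data for PFS2. Add a sensitivity analysis that counts subjects lost after a first progression as events on that date, labelled as a lower bound.

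**If follow-up cannot be added.** Report the as-written estimate together with the bound, and state that second progression is observed only in re-treated subjects. Do not make the bound the reported PFS2: it turns PFS2 into PFS for the lost subjects and is biased downward.

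**Cost.** A short follow-up form for what may be a few subjects per cohort, one further Kaplan-Meier run, and an amendment that touches several sections and needs IRB approval under Section 15.3. No treatment changes and no extra subjects are needed. The reported PFS2 is likely to be less favourable.

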11.6.1.2.7 DURATION OF PERIPHERAL BLOOD UNDETECTABLE MINIMAL RESIDUAL DISEASE RESPONSE

Duration of U-MRD response is defined as the interval from the first documentation of undetectable MRD to the earlier of the first documentation of presence of MRD or death from any cause. The Kaplan-Meier estimate for the duration will be based on subjects who achieve U-MRD response. For subjects alive without presence of MRD, it will be censored at the last MRD assessment.

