3 OBJECTIVES AND ENDPOINTS

3.1 STUDY OBJECTIVES

PRIMARY OBJECTIVES

- To assess the rate of undetectable minimal residual disease (U-MRD) in subjects with CLL treated with the combination of ublituximab and umbralisib with either venetoclax, ibrutinib or acalabrutinib

SECONDARY OBJECTIVES

- To assess safety and tolerability of ublituximab and umbralisib with venetoclax, ibrutinib or acalabrutinib
- To determine the time to U-MRD at planned sequential response assessments
- To determine progression free survival and time to second objective disease progression, from time of initiation of ublituximab and umbralisib with venetoclax, ibrutinib or acalabrutinib
- To determine the durability of clinical benefit after treatment discontinuation as measured by duration of peripheral blood U-MRD response and treatment-free survival
- To determine the overall response rate, complete response rate, U-MRD rate, and PFS to re-treatment with ublituximab and umbralisib with venetoclax, ibrutinib or acalabrutinib in subjects who progress following achievement of U-MRD followed by treatment-free observation.

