⁸ For women of childbearing potential: Serum pregnancy test within 3 days prior to Cycle 1/Day 1; Urine pregnancy tests on Day 1 of each treatment cycle +/- 7 days.

¹⁰ Radiology assessment should include a contrasted CT or MRI imaging of neck, chest, abdomen, and pelvis. For initial treatment, scans to be completed within 30 days prior to Cycle 1 / Day 1. All tumor evaluations post baseline assessment should be performed within 14 days of cycles 3, 6, 12, 18 and 24.. Follow up CTs to be done at investigator discretion/ per standard of care. At the time of response assessment, bone marrow to be performed as per standard of care if other criteria for complete remission are met. CR should only be confirmed once by bone marrow assessment at planned tumor assessments.

¹¹ If U-MRD is confirmed, subjects will complete treatment through the end of that 28-day cycle then return for their first TFO at the subsequent Cycle.

***EOS = End of Study** – EOS visit occurs if subject is discontinuing from the study. Please see Section 5.6 Discontinuation from study , which outlines reasons subject must discontinue from study.

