11.6.1 STATISTICAL ANALYSES

11.6.1.1 PRIMARY EFFICACY ENDPOINT

Best overall U-MRD rate will be reported as well as a proportion during cycles 3, 6, 9, 12, 15, 18, 21 and 24. The U-MRD rate is defined as the proportion of subjects with detectable MRD at baseline who convert to U-MRD in the peripheral blood on two sequential peripheral blood studies at least 4 weeks apart post-baseline. Subjects with detectable MRD at baseline who do not have an MRD assessment at any post-baseline visits will be considered non-responders and will be included in the denominator when calculating U-MRD rate. The 95% confidence intervals (Clopper-Pearson) for the MRD negativity rate will be presented.

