11.6.1.2.1 TIME TO UNDETECTABLE MINIMAL RESIDUAL DISEASE

Time to undetectable minimal residual disease is defined as the interval from enrollment to the first assessment of U-MRD. It will be estimated by the Kaplan Meier method. For subjects who do not achieve U-MRD, it will be censored at the last MRD assessment.

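### Duration of U-MRD is meant to show durability after treatment stops, but its clock starts at the first undetectable sample, which is usually taken on treatment and need not be confirmed

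*Combined protocol and SAP*

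**What the plan says.** The objective, in Section 3.1 and in the synopsis, is: "To determine the durability of clinical benefit after treatment discontinuation as measured by duration of peripheral blood U-MRD response and treatment-free survival".

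Section 11.6.1.2.7 starts the clock as follows: "Duration of U-MRD response is defined as the interval from the first documentation of undetectable MRD". It runs "to the earlier of the first documentation of presence of MRD or death from any cause". The analysis set is given in one sentence: "The Kaplan-Meier estimate for the duration will be based on subjects who achieve U-MRD response". Section 3.2 and the synopsis use the same start and end. None of the three places says that the starting sample must be confirmed or that the subject must be off treatment.

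Confirmation is required elsewhere. The primary endpoint (Section 11.6.1.1) counts subjects who "convert to U-MRD in the peripheral blood on two sequential peripheral blood studies at least 4 weeks apart post-baseline". Stopping treatment also depends on a confirmed result (synopsis; Section 5.2). Footnote 11 of Section 7.1 then sets the stopping date: "If U-MRD is confirmed, subjects will complete treatment through the end of that 28-day cycle then return for their first TFO".

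Two other endpoints bear on this:
- Time to U-MRD (Section 11.6.1.2.1) also uses the first negative: "Time to undetectable minimal residual disease is defined as the interval from enrollment to the first assessment of U-MRD".
- Treatment-free survival (Section 11.6.1.2.8), the other measure named in the objective, starts at drug discontinuation.

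**The concern.** There are two faults, and they act in opposite directions.

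**Time origin.** The objective concerns what happens after the drugs stop. For most responders the duration clock starts while all three drugs are still being taken. It runs through the wait for confirmation and on to the end of that cycle. This on-drug time is added to the reported durability, and the two measures of one objective have different starting points.

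**Confirmation.** A subject whose first negative is not confirmed stays on treatment and continues to be tested, so the sequence negative, positive, then confirmed negative is one that the protocol allows. Read literally, the duration rule starts at the first, transient negative and ends at the positive repeat. A later confirmed remission, however long it lasts off drug, does not count.

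The endpoint is meant to show how long undetectable MRD persists once treatment is stopped on MRD grounds. Treatment-free survival cannot replace it, because retreatment is not triggered by MRD positivity (Section 5.2).

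**Working it through.** The plan gives no expected duration, event count or power for this endpoint, so there is no figure to reproduce. The calendar below follows from the plan's own rules.

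**Inputs**
- Cycles of 28 days; on-treatment MRD in Cycles 3, 6, 9, 12, 15, 18, 21 and 24 (Section 7.1, footnote 7).
- Repeat sample about 4 weeks after a negative, taken as 28 days (same footnote).
- Treatment to the end of the confirmation cycle (Section 7.1, footnote 11), with at most 24 cycles (Section 5.2).
- MRD in treatment-free observation (TFO) about every 12 weeks, taken as 84 days. None is scheduled at the first visit, TFO1, except for subjects who stopped for toxicity (Section 7.2 and its footnote 4).

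**On-drug days counted as duration**

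Let the first negative, later confirmed, fall on day d of its cycle.
- Cycles 3 to 21: the repeat is on day d of the next cycle and treatment runs to the end of that cycle. On-drug days = 57 − d, which is 56 for d = 1 and 29 for d = 28.
- Cycle 24: treatment ends with that cycle. On-drug days = 29 − d, which is 28 for d = 1 and 1 for d = 28.
- Stopped for toxicity and first negative at TFO1: possibly 0.

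**A relapse found at the first scheduled TFO MRD test (Cycles 3 to 21)**

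| First negative | On drug | Off drug | Recorded duration | On-drug share |
|---|---|---|---|---|
| Day 1 | 56 | 84 | 140 | 56/140 = 40% |
| Day 28 | 29 | 84 | 113 | 29/113 = 26% |

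The 84 days come from the sampling interval. With the clock started at discontinuation, this relapse is recorded at 84 days, and there is still no scheduled MRD test before then. With the 14-day visit window, the recorded range of 113 to 140 days widens to 99 to 154.

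**A transient negative, traced through the rules**

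Take all samples on Day 1: negative in Cycle 3, positive in Cycle 4, negative in Cycle 6, confirmed in Cycle 7. Treatment stops at the end of Cycle 7. Assume that MRD is detected 168 days later. Counting from Cycle 1 Day 1 as day 0, these fall on days 56, 84, 140, 168, 196 and 364.
- Literal rule: 84 − 56 = 28 days, an event on treatment.
- From the first sample of the confirmed pair: 364 − 140 = 224 days.
- From discontinuation: 364 − 196 = 168 days.
- Time to U-MRD is dated 140 − 56 = 84 days too early.

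**How much one such subject matters**

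With n responders and no earlier censoring or event, each such subject lowers the Kaplan-Meier curve at 4 weeks by 1/n. That is 12.5, 7.1 or 5.0 percentage points for 8, 14 or 20 responders. These counts are assumed; the synopsis allows up to about 28 subjects per cohort.

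The plan gives no frequency for the pattern. If the chance per responder were 2%, 5% or 10% (assumed, and independent), the chance of at least one among 14 is 1 − (1 − q)^14 = 25%, 51% or 77%.

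**The case against.** The other side has five arguments.

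- **Convention.** Dating a response from the first of its two samples is common practice, and the added time is bounded. This stands as a reason to keep that version as supportive. It does not make it a measure of durability after discontinuation, and the text does not limit the start to a confirmed pair.
- **Analysis set.** If a U-MRD response in Section 11.6.1.2.7 carries the two-sample meaning of Section 11.6.1.1, a subject whose only negative is unconfirmed is not in the analysis. A reader might infer that every unconfirmed negative becomes a false 4-week relapse. The documents support that only if the two-sample rule is set aside. Under either reading, the subject with a later confirmed response is still mis-scored.
- **Source of the flat curve.** A reader might blame the definition for the whole 16 to 20 weeks without a scheduled chance of an MRD event. Only the 4 to 8 on-drug weeks come from the definition.
- **Other off-treatment evidence.** Treatment-free survival already starts at discontinuation, and progression-free survival, PFS2 and the retreatment outcomes also bear on the stopping strategy. One outcome is redacted in Section 11.6.1.2, so it cannot be claimed that the strategy has only two measures. What stands is narrower: treatment-free survival does not measure MRD.
- **Consequence.** This is a secondary endpoint with no visible test or decision rule, and the primary rate already requires confirmation. That limits the severity.

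**Conclusion.** The concern holds in a bounded form. The stated rule for duration of U-MRD does not match the objective it serves, and it omits the confirmation that the primary endpoint requires.

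- For a confirmed responder first negative in Cycles 3 to 21, about 29 to 56 on-drug days count as durability. It would be wrong to apply that range to every responder: it is about 1 to 28 days for a first negative in Cycle 24, and possibly none after stopping for toxicity.
- A transient negative followed by a later confirmed U-MRD is recorded as an event at about 28 days, with time to U-MRD dated to the transient negative. The text permits this pattern, but nothing in the documents shows how often it would occur.

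The day counts assume 28-day cycles, a repeat at exactly 28 days and visits on schedule. This should be corrected before analysis. It does not affect the primary endpoint.

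**What to change.** - **Analysis set:** state that it is subjects with confirmed U-MRD, meaning two sequential samples as in Section 11.6.1.1.
- **Durability objective:** in confirmed responders who stop treatment, report time from the last dose of study treatment to first detectable MRD or death. Where confirmation comes after the last dose (Cycle 24 or toxicity stops), say in advance how the interval before confirmation is handled.
- **Supportive analysis:** keep duration from the first sample of the confirmed pair, counting only MRD detected after confirmation.
- **Time to U-MRD:** take as the event date the first sample of the confirmed pair.
- **Alignment:** make the same changes in the synopsis endpoints and Sections 3.2, 11.6.1.2.1 and 11.6.1.2.7.

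The cost is wording in the protocol and analysis plan. No new samples or visits are needed, since the dates are already collected. Reported durations will be shorter by up to about 8 weeks, and the 12-week gap before the first scheduled off-treatment MRD test will remain.
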